One of the promising ways of addressing all the severe asthma phenotypes may be via targeting one of the upstream inflammatory responses of the disease, such as the cytokine thymic stromal lymphopoietin (TSLP)[13]. TSLP is expressed by the airway epithelium in response to both allergic and non-allergic eosinophilic inflammation [14]. Lack of effective therapies for all patients with severe asthma, together with additional hurdles, such as accessibility or eligibility for more

Study Protocol: [OPCG-2005] Biologic Usage Patterns, Clinical Outcomes and Healthcare Resource Utilization (CLEAR)

than one biologic, have led to patients receiving sub-optimal or inappropriate biologics at initiation [11,12]. This can lead to various patterns of use, such as stopping or switching from the first biologic to a second, and in some cases, to a third or fourth biologic as clinicians and patients search deliberately for adequate response.

In an ISAR study on Biologic Utilization (prepublication) most patients (79%; 2791/3531) continued their first biologic, 10% (356/3531) stopped and 11% (384/3531) switched among patients who were followed up for at least a period of 6 months. This pattern was reproduced at the country level, although the ratio of 'stoppers' to 'switchers' varied. The most common reported reasons for stopping or switching a biologic was lack of efficacy benefits and/or adverse events. Disruption to the clinical management of biologics, most likely due to ineffective response and/or inappropriate initiation of the , may lead to a worsening of asthma control and an associated increase in health care utilization. This has yet to be demonstrated in a real-world setting or quantified. In addition, there may be a subgroup that is eligible yet is not reaping the benefits of targeted therapy.

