#### 2.3 DATA SOURCE

The ISAR registry is a multi-country, multi-center, observational epidemiologic data repository with retrospective and prospective data of patients treated with 2018 Global Initiative for Asthma (GINA) Step 5 or uncontrolled on GINA Step 4 treatment regimens. ISAR holds standardized, patient-level, fully anonymized data for ~9,654² (as of November 2020) patients with severe asthma from 19 national registries (Argentina, Australia, Bulgaria, Canada, Colombia, Denmark, Greece, India, Ireland, Italy, Japan, Kuwait, Mexico, Saudi Arabia, South Korea, Spain, Taiwan, UAE, UK and United States). The data is collected specifically for severe asthma research. All data contributors enter data via electronic Case Report Forms (eCRF) on a web-based platform customized for real-life data collection or within specialized electronic medical records. The reason for either stopping or switching the first biologic is also collected, when applicable [4]. Patient recruitment started in December 2015 Ethical governance for ISAR is provided by The Anonymous Data Ethics Protocols and Transparency (ADEPT) committee, an independent body of experts and regulators commissioned by the Respiratory Effectiveness Group (REG). The registry's scientific merit is ensured by the ISAR steering committee (ISC) that is made up of 48 severe asthma specialist or database experts from 25 countries (http://isaregistries.org/)

<sup>2 This does not include the 671 patients from the Australian Severe Asthma Network that was received on the 1st of Dec. as it is undergoing data quality assessments at the moment.

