#### 2.4 FEASIBILITY

Optimum Patient Care Global
Study Protocol: [OPCG-2005] Biologic Usage Patterns, Clinical Outcomes and (CLEAR)

The diagram above shows the feasibility for the CLEAR study. Overall, 3,532 patients were eligible for the study. Most of them had initiated biologics and continued on them.

[figure not shown]

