First the demographic and clinical characteristics as mentioned in section 3.1 will be described in detail per group. This will include describing proportions on patients from each group based on their biomarkers, long term OCS (LTOCS) use, baseline demographics such as those outlined in Section 3.1. Next, the significant difference in level of T2 phenotypes and demographic or clinical characteristics (section 3.1) across the five groups will be compared and tested for statistical significance via Chi-square tests for comparison of counts data, and t-test or one-way analysis of variance (ANOVA) for continuous variables. Where appropriate, McNemar tests, paired t-tests will be considered. Statistical significance will be defined as p <0.05. Stata version 14.2 (College Station, TX, USA) will be used to conduct all statistical analyses and data manipulations.

Additionally, comparisons will be made as follows:

Study Protocol: [OPCG-2005] Biologic Usage Patterns, Clinical Outcomes and Healthcare Resource Utilization (CLEAR)

- 1. Switch vs. continue
- 2. Stop vs. continue
- 3. Patient received biologics vs. eligible but did not receive biologics
- 4. Biologic eligible (biologic users+ non-users but who qualify) vs. not eligible.

#### 4.2 OBJECTIVE 2

As there are various factors underpinning the probability of not receiving, receiving, continuing, switching, or stopping a biologic, comparing the clinical outcomes set forth in section 3.2 will need careful consideration. One of the main confounders to consider is the availability and/or accessibility of multiple biologics in a country. Therefore, all countries included in the analysis of assessing the clinical outcomes across biological utilization groups will have at least 2 biologics available in the market (availability defined as licensed in the country) at the time of the patient's enrolment into ISAR (index date). There will be a cut-off date of 01 Jan 2014 for assessment of clinical outcomes to ensure the availability of drugs in the market.

Furthermore, according to the results of objective 1 (pre-therapy or baseline characteristics), before assessing for differences in the clinical outcomes across groups, baseline imbalance will be examined across groups and matched accordingly. Prior to this step, the clinical outcomes of each group will be described.

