**Primary outcome: Exacerbation** 

An asthma exacerbation will be defined as the occurrence of the following events (ERS/ATS task

force definition):

asthma-related hospital attendance/admission primary care consultation; AND/OR

asthma-related A&E attendance; AND/OR

an acute oral corticosteroid course of 3 days or more

separate recordings of exacerbations within a 14 day period will be treated as the

same exacerbation.

A time-to-event analysis will be performed to analyse the association between utilization pattern and time to first exacerbation with right censoring at the time of death, switching, stopping or loss to follow-up. Kaplan-Meier curves will be used to describe event-free survival over time and comparisons. Conditional Cox regression will be performed with time to the first exacerbation as the outcome variable (y) to estimate Hazard Ratios (HR) with 95% confidence intervals (CI) of the main effect. The proportional hazard assumption will be evaluated visually by means of a log-log

plot of survival.

As the dispersion of the exacerbation data is expected to be high and as this outcome is conditional on the duration of follow-up, we may apply a negative binomial regression (NBR) to estimate the reduced rate of exacerbation (y=annual rate of exacerbation). We switch to a count model to take advantage of all exacerbations at follow up. Group comparisons (e.g. gender, BMI, number of biologics available etc.) will be made if interaction between a group and biologic use pattern is found. We will also run a NBR using the total post-therapy/post-ISAR enrolment

exacerbations.

Secondary outcome: Asthma control

By applying a multinomial regression model (ordered), we will assess the probability or odds of the combined categories partially or controlled versus uncontrolled asthma for those that continue

compared to those that do not initiate or switch or stop.

Secondary outcome: long term oral corticosteroid (OCS) dose

20

Study Protocol: [OPCG-2005] Biologic Usage Patterns, Clinical Outcomes and Healthcare Resource Utilization (CLEAR)

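### Country-level access is named as a main confounder but handled only by restricting which countries enter; the matching list and the outcome models name no country term, stratum or allowance for clustering

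*Protocol*

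**What the plan says.** Section 2.3 describes the source as a "multi-country, multi-center, observational epidemiologic data repository" holding "patients with severe asthma from 19 national registries". The same sentence names 20 countries, and the title table lists 22 countries of study. Under Feasibility: "Overall, 3,532 patients were eligible for the study".

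Section 4.2 states: "One of the main confounders to consider is the availability and/or accessibility of multiple biologics in a country". It answers this by requiring that countries in the outcome analysis "will have at least 2 biologics available in the market", with availability defined as being licensed. Section 2.1 already has nearly the same condition as an inclusion criterion.

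Section 4.2 then plans to examine baseline imbalance using the Objective 1 results, match on propensity score, recheck standardized mean differences, and enter any residual confounders in the outcome models. The Objective 1 variables are those of Section 3.1, Table 2: patient attributes, diagnostic measurements, therapy and comorbidities. Neither country nor centre is among them.

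For exacerbations the protocol plans a conditional Cox model, without saying what it conditions on, and then "we may apply a negative binomial regression (NBR) to estimate the reduced rate of exacerbation (y=annual rate of exacerbation". Asthma control gets an ordered model. None of the three names country. The number of biologics available appears only as a possible interaction factor. The one correlation that the protocol addresses is within patient, for long-term OCS dose.

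On variation between countries, the Background says of the earlier registry study: "This pattern was reproduced at the country level, although the ratio of 'stoppers' to 'switchers' varied".

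**The concern.** Restricting to countries with two or more licensed biologics does not remove the confounder that the protocol describes. Licensing is not access, so the accessibility half of the statement is untouched. Countries above the threshold can still differ in how many biologics they offer and how readily patients obtain them; the protocol recognises this when it keeps the number available as a possible interaction factor.

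The outcome side may also differ by country or registry. Exacerbations are defined partly through hospital and A&E contacts. Exacerbation dates and rescue-steroid details are bolt-on rather than core variables (Table S2). The asthma control instrument can depend on registry preference (footnote to Table S1).

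If both sides differ by country, a model without country credits part of the country difference to the usage pattern. The hazard and rate ratios are then off for the countries actually studied. Viewed over possible sets of countries, the nominal 95% intervals cover less than 95%.

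**Working it through.** **The plan's own figures.** The protocol gives no power calculation, intracluster correlation (ICC) or standard error, so there is no design figure to reproduce. The one related set of percentages, "continued their first biologic, 10% (356/3531) stopped and 11% (384/3531) switched", checks: 2791/3531 = 79.0%, 356/3531 = 10.1%, 384/3531 = 10.9%, and the counts sum to 3531.

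**Can country enter through the steps as written?**
- *Matching:* drawn from Table 2, which lacks country, so matched patients may come from different countries.
- *Residual confounders:* found by rechecking the same baseline variables, so country would not be flagged unless added.
- *Conditional Cox:* if it conditions on matched sets, a country effect on the baseline hazard cancels only when the sets lie within one country.

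**Approximate variance inflation.** For a patient-level exposure in clusters of average size m:

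DEFF = 1 + (m − 1) × ICC(exposure) × ICC(outcome)

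With 20 countries, m = 3,532/20 = 176.6 (161 with 22 countries, 186 with 19). All ICCs are assumed.
- Exposure ICC 0: DEFF 1.00 at any outcome ICC, so no narrowing.
- 0.01 and 0.05: 1 + 175.6 × 0.0005 = 1.09; SE ratio √1.09 = 1.04; coverage 94.0%.
- 0.05 and 0.05: 1 + 175.6 × 0.0025 = 1.44; SE ratio 1.20; coverage 89.8%.
- 0.10 and 0.05: 1 + 175.6 × 0.005 = 1.88; SE ratio 1.37; coverage 84.7%.
- 0.20 and 0.10: 1 + 175.6 × 0.02 = 4.51; SE ratio 2.12; coverage 64.4%.

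A matched set is smaller. If 356 + 384 = 740 stoppers and switchers were matched 1:1 (1,480 patients, m = 74), ICCs of 0.05 and 0.05 give 1 + 73 × 0.0025 = 1.18, and 0.20 and 0.10 give 1 + 73 × 0.02 = 2.46.

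**Simulation of the negative binomial model.** Assumptions: 20 equal countries, about 3,532 patients, 21% exposed, no true effect, dispersion 1, mean 1.2 exacerbations per year, 250 runs per setting. Each cell shows true SE/reported SE, then coverage of the 95% interval.

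| Country SD, log-odds of usage | Country SD, log rate | No country term | Country fixed effects |
|---|---|---|---|
| 0 | 0.3 | 1.05, 93.6% | 1.03, 93.6% |
| 0 | 0.5 | 1.01, 94.4% | 1.01, 96.8% |
| 0.3 | 0.3 | 1.06, 92.8% | 1.03, 94.0% |
| 0.3 | 0.5 | 1.12, 94.4% | 0.93, 96.8% |
| 0.6 | 0.3 | 1.15, 90.0% | 0.93, 97.6% |
| 0.6 | 0.5 | 1.47, 78.4% | 1.07, 94.4% |
| 1.0 | 0.3 | 1.53, 78.8% | 1.01, 94.0% |
| 1.0 | 0.5 | 2.00, 68.4% | 1.05, 94.0% |

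Monte Carlo error is about √(0.95 × 0.05/250) = 1.4 points for coverage near 95%, and about 1/√(2 × 250) = 4.5% for the ratios, so small departures from 1 are noise.

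The country term works mainly by steadying the estimate, not by widening the interval. In the last row the empirical SD of the estimate falls from 0.1193 to 0.0612, while the mean reported SE barely moves (0.0595 to 0.0581). That is how removing confounding behaves.

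**A second simulation** (400 runs per setting, about 3,500 patients, 20 countries of unequal size) agrees in direction. At nominal 5%, the plain model's type I error was about 8–16% for stopped/switched versus continued (usage SD 0.5–0.8, log-rate SD 0.3) and 23–39% for initiation (usage SD 1.0, log-rate SD 0.3–0.5). A country term brought it to about 3–4%. With centre variation added it was 14–31%, falling to about 6–9% with a country term and centre-robust errors.

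**The case against.** The strongest reply is that this argues from silence. The protocol names model families without covariate lists, nowhere says that patients are independent, and leaves openings: an unspecified conditioning set, propensity matching, and entry of residual confounders. Covariates and variance estimators are commonly left to a SAP, which is not shown. This disposes of any claim that the plan assumes independence. It does not dispose of the point made here. The protocol itself names the confounder, chooses restriction as the remedy, and ties matching to a variable list without country.

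The second reply is that the Background points the other way for stopped or switched versus continued, because the pattern was reproduced by country and only the stopper-to-switcher ratio varied. That stands for the pooled contrast, where variation in the ratio cancels. It is weaker if stopping and switching are each compared with continuing: with a stable continuing share and a varying ratio, the separate shares must vary.

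The third reply is that all the sizes rest on assumed variance components. That stands too. With little country variation in usage (SD 0 to 0.3) the SE ratio is only 1.01 to 1.12.

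**Conclusion.** The point holds in a conditional form. Followed as written, the protocol leaves a confounder that it names itself unadjusted beyond a licensing threshold, and states no allowance for patients being grouped in about 20 registries. The first harm is possible confounding of the usage-pattern estimates by country; intervals that are too narrow may follow. Both need usage and outcome to vary together by country.

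The risk is greatest for initiators versus non-initiators, where country access bears directly on exposure. It is probably small for pooled stopped/switched versus continued. The SE ratio of about 1.0 to 2.0 spans assumed country SDs of 0 to 1.0 (log-odds of usage) and 0.3 to 0.5 (log rate); nothing in the documents places the study within that range.

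A reader might infer that the reported intervals are certainly too narrow, or that error rates of 23–39% should be expected. The documents do not support this: they give no country-level figures for initiation, and what they say about continuing, stopping and switching suggests limited variation.

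**What to change.** In Section 4.2, name country as a design variable for every usage-pattern contrast:
- match within country, or stratify the Cox baseline hazard by country, and state what the conditional Cox model conditions on;
- include country, as a fixed effect or random intercept, in the negative binomial and ordered models, and in the health-resource models that follow the same approach;
- if centre identifiers are available, report centre-robust standard errors;
- tabulate usage pattern and crude exacerbation rate by country, so that the likely size of the problem can be seen.

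The cost is a few lines of text and model options, with no new data if country and centre identifiers are kept. Intervals may become somewhat wider, particularly with centre-robust errors; in the first simulation, country fixed effects alone changed the mean reported SE by between −10% (0.0624 to 0.0564) and +4% (0.0550 to 0.0574). Countries with only one usage pattern will contribute little to that contrast. Within-country matching may lose patients in small countries: on the earlier study's counts the average over 20 countries is 356/20 ≈ 18 stoppers and 384/20 ≈ 19 switchers. Stratification or a country term avoids that loss. Centre-robust errors are not a complete cure, as the remaining 6–9% error in the second simulation shows.

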Standardized mean difference (SMD) will be used to quantify differences in both continuous and categorical variables between the biologic utilization groups at baseline. An SMD  $\leq$  10% indicates sufficient balance between treatment groups. It is hypothesized that data completeness will vary between treatment groups. Therefore, propensity score matching methodology is envisioned at the stage of comparing between groups to conserve the statistical power. After the matching approach, the SMD will be recalculated to verify the accuracy of the model. If residual confounders are present, they will be entered into the respective multivariate model noted below. Clinical and/or health resource outcomes may be affected by the level of eosinophilic phenotypes, thus, results may be stratified by level of ISAR Eosinophilic Grade.

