#### **Group comparisons**

The first set of results for the primary and secondary outcomes (section 3.2) will be demonstrated for those that did not initiate a biologic versus those that did (switch, stop, continue) (initiators

Study Protocol: [OPCG-2005] Biologic Usage Patterns, Clinical Outcomes and

Healthcare Resource Utilization (CLEAR)

versus non-initiators). The second set of results will compare the outcome results for patients that stopped or switched versus those that continued.

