#### Secondary outcome: Health resource utilization

Hospitalizations, invasive ventilations (if available) and emergency room visits will compose the outcome variable of health resource utilization (section 3.2). The difference in the number of incident hospital or emergency room visits in the outcome period across groups will be examined similarly to the primary outcome (exacerbation) discussed above. These outcomes will be considered separately for each healthcare resource and as a combined variable as well.

Study Protocol: [OPCG-2005] Biologic Usage Patterns, Clinical Outcomes and Healthcare Resource Utilization (CLEAR)

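### Subgroup comparisons are shown only when an interaction is found, from an open factor list with no criterion, so the subgroup effects reported are selected on their result

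*Protocol*

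**What the plan says.** The rule is in protocol section 4.2, under the primary outcome, after the negative binomial text: "Group comparisons (e.g. gender, BMI, number of biologics available etc.) will be made if interaction between a group and biologic use pattern is found". Three factors are named as examples and the list is left open. Nothing says what counts as finding an interaction. Earlier in 4.2, "results may be stratified by level of ISAR Eosinophilic Grade", with no interaction test required first.

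The comparisons come in two sets. The first is initiators against non-initiators. For the second: "The second set of results will compare the outcome results for patients that stopped or switched versus those that continued".

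The only significance level is in section 4.1, on Objective 1: "Statistical significance will be defined as p <0.05". Section 4.2 does not repeat it. There the Cox model is "to estimate Hazard Ratios (HR) with 95% confidence intervals (CI) of the main effect".

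Exacerbation is labelled primary; asthma control, long-term OCS dose and health resource utilization are labelled secondary. Exacerbation gets a Cox model, an optional negative binomial model for the annual rate and a further one for total events. Asthma control has its own ordered model and OCS dose its own GLM with GEE. Only utilization is to be handled like the primary outcome, and for it: "These outcomes will be considered separately for each healthcare resource and as a combined variable as well".

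**The concern.** The protocol commits to a selection rule: look for interactions between use pattern and an unspecified set of factors, then present subgroup comparisons for those that appear. Two things follow.

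- The reader sees the interactions that passed and not how many were examined. A chance interaction looks the same as a planned one.
- An estimate that is shown because it crossed a threshold is biased away from the null.

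The open list makes this worse, because factors can be added at any time. The timeline in section 9 places analysis and pilot results in May to August 2021 and protocol finalization in August 2021. That does not show that factors were chosen after results were seen, but nothing in section 4.2 rules it out.

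At stake is the credibility of statements that switching, stopping or not initiating matters more in one kind of patient than in another. Optional stratification by grade adds a second discretionary route to such statements. For utilization, carrying over the exacerbation methods without naming a main model leaves open which of several results is reported first.

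**Working it through.** The protocol states no familywise error rate, so there is no figure of its own to reproduce.

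**Inputs**
- Factors named in the rule: 3 (gender, BMI, number of biologics available), each counted as one interaction test.
- Contrast sets: 2 (section 4.2, Group comparisons).
- Models screened: 1 (assumption; the sentence follows the negative binomial text).
- Threshold: 0.05, two-sided (assumption; borrowed from 4.1 and in line with the 95% CIs).
- Correlation between test statistics: unknown, so shown from 0 to 0.9.
- Eosinophilic grade is left out of the count, because its stratification is not triggered by an interaction.

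**Chance of at least one false trigger when no interaction exists**

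For k independent tests: 1 − 0.95^k. For correlated tests: the probability that any of k equicorrelated standard normal statistics exceeds 1.96 in absolute value.

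- One contrast, k = 3: 1 − 0.95³ = 1 − 0.8574 = 14.3%. At correlation 0.5, 12.5%; at 0.9, 8.4%.
- Two contrast sets, k = 3 × 2 = 6: 1 − 0.95⁶ = 1 − 0.7351 = 26.5%. At correlation 0.5, 20.7%; at 0.9, 10.8%.
- Effect of the open list, if it grew to 10 factors on one contrast (assumption): 1 − 0.95¹⁰ = 40.1%. At correlation 0.5, 28.7%; at 0.9, 12.8%.

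**Exaggeration**

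Take one interaction whose true value is zero and show it only if |Z| > 1.96. The mean size of what is shown is 2φ(1.96)/0.05 = 2 × 0.0584/0.05 = 2.34 standard errors. A true but modest interaction is also inflated by this selection, though by less.

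**Utilization**

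Up to 4 variables are possible: hospitalizations, emergency visits, invasive ventilation if available, and the combination. Over 2 contrast sets, one model each gives 4 × 2 = 8 results. If all three exacerbation models were carried over, there would be 4 × 2 × 3 = 24. The second count is the largest the text allows, not one that it states: one model is optional, ventilation depends on availability, and the wording refers to numbers of hospital and emergency visits. It shows only why a main model should be named.

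**The case against.** The strongest reply is that a factor list, an interaction threshold and exploratory labels are usually left to the SAP, which is not at hand, and that requiring an interaction before showing subgroups is stricter than showing them all. The study is also an observational registry analysis with descriptive aims. Part of this stands: the absence of a multiplicity scheme is not in itself a fault here. But the protocol goes further than silence. It fixes a rule under which presentation depends on the result, and a SAP that reported every factor would have to override it. The interaction requirement limits how many subgroups appear, but it also selects the ones most affected by chance.

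A reader might infer more than the text supports:

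- That all secondary outcomes repeat the primary set of analyses. Only utilization follows those methods.
- That there is no hierarchy. Outcomes are ranked primary and secondary; what is absent is a testing order.
- That everything is tested at 0.05. That level is stated under Objective 1. Reading it as study-wide is reasonable, since the next sentence covers the software for all analyses, but it remains an inference.
- That chance subgroup or utilization claims are likely. The figures for the named factors stay below 30%, and the overlap between models and outcomes makes the correlated end plausible.
- That utilization should be tested only after a positive primary result. Utilization is an objective in its own right (Objective 3), and with several models and contrasts a positive primary result is not defined.

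**Conclusion.** The point holds for the subgroup rule. As written, it produces subgroup effects that are chosen because of their result, from a list that can grow. With the three named factors and no true interaction, the chance of at least one false trigger is 14.3% on one contrast and 26.5% over both contrast sets if the tests are independent, and 8.4% and 10.8% at correlation 0.9. These rest on an assumed two-sided 0.05 threshold, one test per factor and one model; more factors raise them. The inflation is material, but it does not make a false subgroup claim more likely than not. The selection bias does not depend on the exact threshold. For utilization the supported conclusion is narrower: no main model is named.

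**What to change.** In section 4.2:

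- Replace the trigger sentence with a closed list: sex, BMI category, number of biologics available and eosinophilic grade.
- Report the interaction estimate with its 95% CI for every listed factor, whether or not it is significant.
- Label all subgroup and grade-stratified results exploratory.
- For health resource utilization only, name one main model per outcome and present the other models as supportive, with estimates and 95% CIs. Do not make these analyses conditional on a positive primary result.

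The cost is a few sentences and slightly longer tables, with no new data. The downside is that subgroup results cannot be presented as confirmed.
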